#### D. Subject Criteria (See Vulnerable Populations appendix, if applicable)

Participants will be adults 21 years or older who smoked at least 5 cigarettes daily at enrollment and have smoked menthol cigarettes for  $\geq$  6 months. The study will be open to both men and women.

#### **Eligibility Criteria**

Inclusion Criteria	Exclusion Criteria					

 
≥ 21 years of age
 
Smoke ≥5 CPD
 
Smoked menthol cigarettes for ≥ 6 months
 
Verified smoker (CO ≥ 5 ppm)
 
Functioning telephone
 
Interested in switching to EC
 
	
 
Interested in quitting smoking
 
Use of other tobacco products in past 30 days (i.e., cigarillos, cigars, hookah, smokeless tobacco, pipes)
 
EC use on ≥ 4 of the past 30 days
 
Uncontrolled hypertension: BP ≥ 180 (systolic) or ≥ 105 (diastolic)
 
Use of smoking cessation pharmacotherapy in the month prior to enrollment
 
Pregnant, contemplating getting pregnant, or breastfeeding
 
Plans to move from KC during the treatment or follow-up phase
 
Another household member enrolled in the study
 
					

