
#### Statistical evaluation of study aims

#### Aim 1. Compare the effectiveness of menthol versus tobacco EC at facilitating switching at week

**12. Primary hypothesis.** *Participants randomized to tobacco EC (versus menthol EC) will demonstrate non-inferior rates of complete and predominant switching to EC (primary outcome). Complete switching is defined as exclusive use of EC, biochemically confirmed with CO < 6 ppm, and predominant switching is defined as use of EC with > 50% reduction in CPD.* We will test this hypothesis by calculating the 95% confidence interval for the difference in P1-P2, as defined above. To show noninferiority the upper limit of the confidence interval must be greater than or equal to 0.00 and lower limit of the confidence interval must be larger than -0.09. If the upper limit of the confidence interval is less than 0.00 then we cannot conclude noninferiority. If the upper limit is greater than or equal to 0.00 and the lower limit is less than or equal to -0.09 then the results would be inconclusive.

Rates of complete and predominant switching will also be compared separately by group using the chisquare test. Note, that we have not specified an a priori difference threshold for these analyses and, therefore, they are not testing noninferiority and should be considered exploratory. What these analyses will provide is an estimate of the proportion of complete switchers in the tobacco EC versus menthol EC group and, separately, an estimate of the proportion of predominant switchers in the tobacco EC versus menthol EC group.

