#### Inclusion criteria

Inclusion criteria are displayed in the adjoining table. Eligible individuals must be at least 21 years, interested in switching to EC, smoked  $\geq$ 5 cpd, smoke menthol cigarettes for  $\geq$ 6 months, be a verified smoker (CO  $\geq$  5PPM), be willing to complete all visits, and have a functioning telephone number.

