#### **B. Outcome**

#### EFFECTIVENESS (Aims 1 & 4).

Switching (Primary Outcome). The primary outcome is the proportion of menthol smokers who make a complete or predominant switch to EC, defined as use of EC along with a > 50% reduction in cigarettes from baseline to week 12. The 7-day Timeline Follow Back Interview (TLFB) will be used to assess participants cigarette and EC use patterns each day for the past 7 days at each visit (weeks 0, 4, 8, 12, 18, 26). The primary endpoint is, however, fixed at week 12. The TLFB is a reliable and valid way of collecting information about substance use quantity and frequency and, in tobacco research, has been corroborated against interactive voice response, butt counts (storing and returning the butts of cigarettes smoked), and biological measures for cigarettes smoked and puff topography for EC, supporting the strong validity of this self-report measure compared to other 'gold standard' measures. For each of the last 7 days participants will be asked to recall the number of cigarettes smoked and EC sessions vaped; following standard practice, an EC session is defined as at least 15 puffs or lasting around 10 minutes. For each EC session, participants will be asked to specify the device used (i.e., study provided versus something else) and the flavor (i.e., menthol, Virginia tobacco, something else).\* For non-study provided EC, detailed information will be collected about the type of EC (e.g., brand, podbased, disposable, refillable), flavor, nicotine concentration and, if available, whether the product is nicotine salt-based. To aid in recall and corroborate self-report, participants will be given dated bags to collect all EC. Bags will be returned at each visit during the intervention phase and used to confirm use of study provided EC (i.e., grams of e-liquid consumed) and protocol adherence (i.e., the number of pods vaped in the study provided versus non-study provided flavor). *Complete switching* is defined as any use of EC and no use of cigarettes in the past 7 days (i.e., 100% reduction in CPD from baseline), biochemically confirmed with an expired breath CO < 6 parts per million (ppm). CO is used for verification because cigarettes produce carbon monoxide as a byproduct of combustion, while heating an e-liquid does not generate CO. The < 6 ppm CO cutoff is more conservative than the  $\leq$  10 ppm cutoff that is commonly used and reflects the current state of knowledge for detecting recent cigarette smoking. Predominant switching is defined as those who report any use of EC along with a > 50%reduction from baseline in CPD. A > 50% reduction has been selected because it is a measure of acceptability of the EC products and is associated with substantial reductions in biomarkers of harm and exposure relative to continued smoking and is a common endpoint used in tobacco harm reduction studies. Partial switching will be defined as those who report any use of EC along with a  $\leq$  50% reduction from baseline in CPD. No switching (i.e., exclusive cigarette user) will be defined as those who reported no use of ECs and any use of cigarettes in the past 7 days. A potential fourth group, no use of e-cigarettes or combustible cigarettes, may occur. For all switching trajectories, use of EC will be corroborated with pod counts and objectively measured EC pod weights during the intervention phase.

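### The entry CO rule (5 ppm or more) and the complete-switching CO rule (below 6 ppm) overlap, so for people who enter in the shared band CO cannot expose a false report of no cigarettes

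*Combined protocol and SAP*

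**What the plan says.** **Entry.** The Eligibility Criteria table in Section II.D lists "Verified smoker (CO ≥ 5 ppm") among the inclusion criteria, and the Inclusion criteria text beneath it repeats the same threshold. Entrants must also smoke at least 5 cigarettes per day (CPD) and have smoked menthol cigarettes for at least 6 months.

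**Complete switching.** Section V.B, under effectiveness, says that this category "is defined as any use of EC and no use of cigarettes in the past 7 days", and that it is "biochemically confirmed with an expired breath CO < 6 parts per million (ppm"). The same cutoff appears in Sections I.A, II.B and II.C (Aim 1). Section V.B explains it: the cutoff is stricter than the one in common use and "reflects the current state of knowledge for detecting recent cigarette smoking". The entry cutoff is given no rationale.

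**Predominant switching.** "Predominant switching is defined as those who report any use of EC along with a" fall in CPD of more than 50%. CO is not part of this definition.

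**Where these enter the analysis.** "The primary outcome is the proportion of menthol smokers who make a complete or predominant switch to EC". Section II.C (Aim 1) also compares complete and predominant switching separately, and says of those tests that "they are not testing noninferiority and should be considered exploratory". Aim 4 looks at complete and predominant switching again at week 26.

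**The concern.** The two CO rules answer opposite questions, so one would expect them not to accept the same reading. They do. By the rationale in Section V.B, a reading of 5 ppm does not indicate recent smoking. By Section II.D, the same reading verifies a smoker.

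What is at stake is the meaning of a CO-confirmed complete switch. CO is the only biochemical check on abstinence from cigarettes. Pod counts and weights corroborate e-cigarette use, not the absence of cigarettes, and only during the intervention phase. The trial is open label and staff encourage participants to adopt the e-cigarette, so some over-reporting of abstinence is a reasonable worry. Someone who entered at 5 ppm already satisfies the CO part of complete switching before receiving any product. If that person later reports no cigarettes, an unchanged reading adds no evidence that the report is true.

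**Working it through.** **1. Does the plan's own sample-size figure depend on CO?** Inputs from Section II.C: 400 per group, menthol rate 0.73, margin 0.09, Type 1 error 2.5%. With equal true rates and an unpooled normal approximation:

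power = Φ(0.09 / √(2 × 0.73 × 0.27 / 400) − 1.96) = Φ(0.09 / 0.0314 − 1.96) = 0.818.

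This matches the stated 82%. No CO quantity enters, so nothing below changes the sample size or the power.

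**2. Set the two rules side by side.**

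| CO reading (ppm) | Entry rule (≥ 5) | Confirmation rule (< 6) |
|---|---|---|
| 4 | fails | passes |
| 5 | passes | passes |
| 6 or more | passes | fails |

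The overlap is 5 ≤ CO < 6. It is the single value 5 if the device reads in whole ppm, which is an assumption because the documents do not state the resolution. With entry at 6 ppm or more and confirmation below 6 ppm, the overlap is empty.

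**3. Apply the Section V.B definitions to a continuing smoker who also uses the e-cigarette.**

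| Report at week 12 | CO (ppm) | Complete | Predominant criterion met | Counted in primary composite |
|---|---|---|---|---|
| Unchanged smoking, reported honestly | 5 | no | no | no |
| Zero cigarettes, reported falsely | 5 | yes | yes | yes |
| Zero cigarettes, reported falsely | 6 or 15 | no | yes | yes |

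The last two rows differ only in the complete-switching column. A reported 100% reduction exceeds 50%, so the person counts in the composite whatever the CO reading.

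**4. How many people?** The documents give no baseline CO distribution. Assume that 1% to 10% of the 800 participants enter in the band: 0.01 × 800 = 8 and 0.10 × 800 = 80. These are people for whom an unchanged reading is uninformative, not people misclassified. Assume further that 2% to 10% of them falsely report abstinence. That gives 0.02 × 8 = 0.16 at the low end and 0.10 × 80 = 8 at the high end, over both arms. The high end is 8 / 800 = 1 percentage point on the overall complete-switching rate.

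**5. Direction for the comparison of complete switching.** If a fraction f of those who are not true complete switchers is wrongly confirmed in each arm, a true rate p is observed as p + f(1 − p). The difference between arms becomes (1 − f)(P1 − P2), where P1 and P2 here are the true complete-switching rates. It shrinks toward zero by the fraction f. At the top of both assumed ranges f = 0.10 × 0.10 = 0.01, so the shrinkage is 1% of the true difference.

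**The case against.** An entry screen and an outcome check serve different purposes and need not share a cutoff. A lower entry threshold could be meant to include light smokers. That is a fair position, but the documents do not take it, and it would not restore the check for people who enter in the band.

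A reader might infer that an unchanged smoker can be recorded as a complete switcher on CO alone. The documents do not support this. The person must also report e-cigarette use and, day by day on the 7-day timeline follow-back, falsely report no cigarettes. An honest continuing smoker at 5 ppm is in neither switching category. Nor does 5 ppm admit anyone as a smoker by itself, since the CPD and menthol-history criteria also apply.

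A reader might also infer that complete switching is the only category with any objective check. It is the only one with a CO check. Section V.B applies pod counts and weights to every switching category during the intervention phase.

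It can further be said that aligning the cutoffs cures little: a person who enters at 6 ppm, keeps smoking, reads 5 ppm at week 12 and reports zero cigarettes would still be confirmed. This stands. CO discriminates poorly just above the cutoff, and alignment removes only the band in which it is uninformative from the outset.

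Finally, the size rests on assumption. Section V.B does describe the sample, in its rationale for a dependence item, as mainly people smoking 10 or fewer cigarettes a day. That makes low entry readings plausible but does not show clustering at 5 ppm.

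**Conclusion.** The concern holds as a narrow, unreconciled inconsistency. Readings from 5 to below 6 ppm count both as verifying a smoker and as confirming no smoking. For people who enter in that band, complete-switcher status at weeks 12 and 26 rests on self-reported abstinence. On the assumed 1% to 10% share, that is 8 to 80 people. Those actually misclassified would be the smaller number who also misreport.

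The consequence is limited to the complete-switching rate, in an exploratory comparison at week 12 and in part of Aim 4 at week 26. A stronger reading, that the overlap biases the non-inferiority conclusion, is not supported: on the literal definitions the primary composite is the same whatever the CO reading. That rests on classing someone who reports zero cigarettes but fails CO as a predominant switcher, which the documents do not say outright. If such people were counted as non-switchers, the overlap could reach the primary outcome.

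**What to change.** Reconcile the two cutoffs so that no reading counts as both.

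- **If enrolment has not started:** for example, set the entry criterion at CO of 6 ppm or more in both the Eligibility Criteria table and the Inclusion criteria text, and keep confirmation below 6 ppm. The cost is a short amendment and a few light smokers excluded or re-tested.
- **If enrolment has started:** leave eligibility unchanged and add one sensitivity table of complete switching at weeks 12 and 26, by arm, among participants with baseline CO of at least 6 ppm. Baseline CO is already collected at week 0 and precedes randomization, so the restriction does not select on anything the assigned flavor could have changed. The cost is one table.

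Either way, some weakness of CO just above the cutoff remains and should be acknowledged when the CO-confirmed rate is reported.

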#### Inclusion criteria

Inclusion criteria are displayed in the adjoining table. Eligible individuals must be at least 21 years, interested in switching to EC, smoked  $\geq$ 5 cpd, smoke menthol cigarettes for  $\geq$ 6 months, be a verified smoker (CO  $\geq$  5PPM), be willing to complete all visits, and have a functioning telephone number.

#### **Exclusion criteria**

Exclusion criteria are also displayed in the adjoining table. Individuals who are interested in quitting smoking will be excluded and referred to smoking cessation resources. Other exclusions include individuals who have used EC on at least 4 of the past 30 days, uncontrolled hypertension (BP  $\geq$  180 (systolic) or  $\geq$  105 (diastolic)), anticipated or current pregnancy (as measured by over-the-counter pregnancy test kit for women of childbearing age only), breast feeding. Other exclusions include use of stop smoking medications in the past 30 days, daily use of other nicotine or tobacco products, plan to move from the Kansas City area in the next year, or other smoker in household enrolled in the study.

#### Withdrawal/Termination Criteria

There are no expected circumstances in which the subject's participation will be terminated by the investigator.

# *Clarify whether a study subject may participate in another research study while participating in this research study*

Subjects are not able to participate in a smoking cessation research study while they are enrolled in the current study.

#### E. Specific methods and techniques used throughout the study

#### Laboratory tests

Not more than 20 ml of urine and saliva will be collected at Weeks 0, 12 and 262. The urine and saliva will be banked for future analyses.

#### Study Procedures:

#### Intervention

All eligible participants who provide written informed consent and complete the baseline survey will be randomized in a 1:1 fashion to either menthol or Virginia tobacco EC.

#### **Treatment Overview.**

**Randomization.** All eligible participants who provide written informed consent and complete the baseline survey will be stratified by race and gender and randomized 1:1 to either menthol or Virginia tobacco EC. Randomization will be determined by computer-generated random numbers. Randomization assignments will be placed in sealed envelopes with sequential study ID numbers. After baseline data collection has been completed, the research assistant will select the sequential study ID number to determine the randomization assignment.

**EC (Weeks 0-12).** Participants will be provided a 12-week supply of VUSE 5% nicotine concentration in either menthol or Virginia tobacco that will be dispensed at the weeks 0, 4, and 8 in-person visits (4-week supply @ each visit). One pod delivers the equivalent of one pack of cigarettes, with variability of 13-30 cigarettes based on user,  and therefore allocation will be based on 1 pod per pack of cigarettes at week 0 and on current use patterns at weeks 4 and 8.

**EC use.** Participants will be instructed to use only the study EC in the flavor provided but to report all ECs by timeline follow-back at follow-up visits. To aid in recall and assessment of fidelity to protocol, participants will be given dated bags to collect all EC. Bags will be returned at each visit during the intervention phase to confirm use of EC (i.e., grams of e-liquid consumed and count of pods) as well as protocol adherence (i.e., the number of pods/grams vaped in the study provided versus non-study provided flavor) (see Measures). Those not attending EC dispensing visits will be reached by phone and delivered enough to get them to the next dispensing time point. Participants will be compensated for returned pods, but earnings will not be tied to protocol adherence. Participants will be paid for returned pods even if they return non-study provided EC to increase honest reporting.

#### **Procedures and Methods**

An overview of major study events is provided in the adjoining table.
---

	Screen*	Enroll						Primary Outcome		
		∘Wk 0	Wk 1*	Wk 2*	Wk 3*	Wk 4	Week 8	Wk 12	Wk 18	Week 26
Remuneration		\$40				\$60	\$60	\$60	\$40	\$40
EC Check-ins		Х	Х	Х	Х	Х	Х	Х		
Dispense EC		Х				Х	Х	Х		
Screening	Х	Х								
Consent		Х								
Assessments		Х				Х	Х	Х	Х	Х
Spirometer		Х						Х		Х
CO		Х				Х	Х	Х	Х	Х
Blood Pressure		Х						Х		Х
Exhaled Breath		х				Х	Х	×		
Condensates								Х		
Urine and Saliva		Х						Х		Х

\* Over the phone

**Initial Screening.** The initial screen will review inclusion/exclusion criteria. Those eligible will be scheduled to complete final eligibility screening within 21 days. All ineligible smokers will be referred to local resources when applicable.

**Final Screening and Enrollment (Wk 0).** Final eligibility screening will be conducted in person and will consist of a pregnancy test on women of childbearing age and obtaining informed consent.

**Electronic cigarettes (Wk 0, 4, 8, 12).** Participants will be provided a 12-week supply of VUSE 5% nicotine concentration in either menthol or Virginia tobacco that will be dispensed at the weeks 0, 4, and 8 in-person visits (4-week supply @ each visit). To aid in recall and assessment of fidelity to protocol, participants will be given dated bags to collect all EC. Bags will be returned at each visit during the intervention phase to confirm use of EC (i.e., grams of e-liquid consumed and count of pods) as well as protocol adherence.

EC Check-in Visits (Wks 0, 4, 8, and 12). Check-in sessions, each lasting approximately 20 minutes, will be completed in person at Wks 0, 4, 8, and 12 and by phone at Weeks 1, 2, and 3. The number of sessions is consistent with our previous studies where we have achieved visit completion rates of ~ 80%.

**Spirometer.** Lung function will be assessed via spirometry. We will carefully monitor respiratory symptoms over time using standardized measures. Spirometry will be completed at Wks 0, , 12, and 26.

**Carbon Monoxide.** Exhaled air carbon monoxide (CO) is an immediate, non-invasive method of biochemically verifying smoking status. At Wks 0, 4, 8, 12, 18, and 26, all participants will breathe into a Micro-3 Smokerlyzer (Bedfont Scientific) for the purpose of determining smoking levels.

**Blood Pressure.** Systolic and diastolic blood pressure will be measured with an Welch Allyn blood pressure cuff at Wks 0, 12, and 26.

**Exhaled breath condensates (EBC).** EBC will be used as another mean to assess airway inflammation. EBCs will be collected using the RTube (Respiratory Research, Inc.). Subjects will breathe in and out through a mouthpiece at tidal volume. A one-way valve will direct the exhaled air through the cooling sleeve where the samples are collected. The collection time will be 10 minutes. Typical condensate fluid yield is 300  $\mu$ /minute for an adult at normal tidal breathing effort. The EBC will be stored in 1 ml aliquots at -80 °C for subsequent analysis. Samples will be standardized by total collected volume. EBC will be used to measure inflammatory patterns using nanobiosensors.

**Retention**. Retention is enhanced by having participants meet with the same study team member each time. We have also developed a system of reminders and compensation for participant efforts that have resulted in impressive retention rates in our previous clinical trials. Reminders. Five days prior to each visit a reminder postcard, email, and/or text noting the scheduled appointment date and time will be sent. Participants will also be called, texted, or emailed (based on preference) up to 6 times to remind them of their upcoming visit. A detailed tracking database, with an automated reminder system, will notify study staff of when to send reminder messages. Compensation. Participants will be compensated in the form of a ClinCard, which works like a debit card. They will receive \$40 at Wks 0, 4, 8, 18, and 26 and \$50 at Week 12 as compensation for their time/travel. To encourage use of the study provided EC, an additional \$20 will be provided at weeks 4, 8, and 12 for returning EC pods, regardless of the flavor returned.

## *Clearly indicate which procedures, tests, visits, etc., are parts of usual standard therapy and which are performed solely for research purposes.*

All tests, procedures, and visits are being performed solely for research purposes and are not billable to insurance companies.

# Describe the fate of any body component (blood, CSF, bone marrow, etc.) used in the study, emphasizing confidentiality of labeling of the sample and the sample's destruction or storage.

Samples will be labeled only with a unique study identification number and only members of Dr.

[name] and [name]'s team will have access to the samples. For participants who have agreed to have their biospecimens stored for future testing, samples will be stored indefinitely.

#### F. Risk/benefit assessment

#### Physical risk

The most common side effects related to EC include cough, dry mouth, shortness of breath, mouth and throat irritation, headache, dizziness, nausea or vomiting, and increased heart rate/palpitations. In rare instances, severe pulmonary disease associated with EC use and death have been noted, but these incidents have primarily occurred in a black-market product that contained tetrahydrocannabinol, or THC, in combination with vitamin E acetate. These additives are not present in the EC used in this study.

